4.3.2 Known Potential Risks

The potential risks of participating in this trial are those associated with having blood drawn, having nasal swabs collected, intramuscular (IM) injection, possible reactions to the study product (GRT-R910), and breach of confidentiality.

Drawing blood may cause transient discomfort and fainting. Fainting is usually transient and managed by having the subject lie down and elevate his/her legs. Bruising at the blood draw site may occur but can be prevented or lessened by applying pressure to the blood draw site for a few minutes after the blood is taken. IM injection may also cause transient discomfort and fainting. Drawing blood and IM injection may cause infection. The use of aseptic (sterile) technique will make infection at the site where blood will be drawn or where the vaccination will be given extremely unlikely.

The nasal swabbing procedure is momentarily uncomfortable but is not otherwise associated with risk. It may cause brief pain, itchy nose, eye watering or sneezing.

4.3.3 Risks of GRT-R910

GRT-R910 has been administered to human participants prior to the initiation of this study. As of 04 October 2021, 13 subjects have received GRT-R910 in the Phase 1 clinical trial (NCT04776317). At the time of initiation of this protocol, safety and immunogenicity are consistent with prior vaccines using the gritstone SAM platform.

Gritstone's preclinical pharmacology and toxicology data have shown an acceptable nonclinical safety profile. No dose-limiting safety signals have been identified in these studies. A toxicology study resulted in minimal safety findings with the most common event in non-human primates being temperature elevation that was transient and self-resolved. As of 06 May 2021, 141 doses of SAM encoding for cancer-associated neoantigens have been administered to 48 cancer patients in ongoing Phase 1-2 clinical trials.

Two mRNA-based vaccines for SARS-CoV-2 have been evaluated in Phase 3 clinical trials and have been authorized for emergency use in several countries, including the US.^{73,74,75,76,77} In August 2021, the US FDA announced full approval of the Pfizer/BioNTech vaccine in the US only. In addition, more than 150 million doses of these mRNA vaccines have now been given to persons in the US alone. In clinical trials of mRNA vaccines, adverse events (AEs) have been quite similar to those observed with adenovirus-based vectors, except for the absence of cases of

vaccine-induced thrombotic thrombocytopenia. Immune mediated thrombocytopenia has also been noted after mRNA vaccines without the clotting component. A small number of cases of anaphylactic reactions have been reported after administration of the authorized mRNA vaccines for SARS-CoV-2. These events are under investigation. It has been proposed that such reactions may be related to the polyethylene glycol (PEG) in the LNP component of these vaccines, which is different in Gritstone's GRT-R910.

Gritstone's heterologous prime-boost vaccines are being developed for the treatment of patients with advanced solid tumors using a SAM vaccine GRT-R902 or GRT-R904 with up to 8 boosts, following a single administration of a ChAd-based prime using either GRT-C901 or GRT-C903. As of 6 May 2021, 48 patients with advanced cancers have been enrolled in Phase 1-2 clinical trials and have received a ChAd-based prime vaccine consisting of either GRT-C901 or GRT-C903 at a fixed dose of 1×10^{12} vp followed by up to 8 SAM boosts of either GRT-R902 or GRT-R904 at doses ranging from 30 to 300 mcg with 10 patients to date receiving the 300 mcg dose as bilateral intramuscular injections. All patients received concomitant doses of intravenous (IV) nivolumab at 480 mg flat dose. Most patients also received concomitant doses of ipilimumab subcutaneously at a 30 mg flat dose. No DLTs related to either the ChAd- or SAM-based vaccines in combination with nivolumab and ipilimumab have been observed at the time of this writing. One patient has experienced a serious adverse event (SAE) of treatment-related Grade 2 fever within approximately 12 hours after GRT-C901 and nivolumab, managed with anti-pyretics and fluids and resolved within 24 hours. Most patients reported transient episodes of low-grade fever, injection-site reactions, chills, nausea, fatigue and generally, flu-like symptoms, within 12 to 24 hours after vaccine administration with either the ChAd- or SAM-based vectors. Three patients presented with elevated serum creatine kinase with 2 patients developing transient signs and symptoms of myositis and rhabdomyolysis. While auto-immune myositis is a known toxicity of nivolumab and/or ipilimumab, the role of the vaccine vectors and/or their antigenic cassettes cannot be formally excluded.

Overall, these symptoms were reversible and generally well tolerated, even in older adult patients with advanced solid tumors. The contribution of nivolumab and ipilimumab to these inflammatory-like responses cannot be excluded. These observations support the administration of the proposed SAM-based vaccine, GRT-R910, encoding antigens of SARS-CoV-2 in healthy subjects at a dose of up to 100 mcg. In the current proposed study, where subjects will have received a first-generation vaccine (prime-boost), lower doses of GRT-R910 are anticipated to be sufficient to boost and expand the initial immune response. Hence, low doses of GRT-R910 will be assessed, specifically 10 mcg and 30 mcg.

Risks to subjects receiving the study products are expected to primarily involve mild to moderate local reactions, which have been observed in animal studies and are generally observed and expected for other IM-administered vaccines. These local reactions may consist of transient and dose-dependent pain, swelling, and erythema. Possible systemic reactions, which are also transient, may include fever, fatigue, chills, headache, myalgia, and arthralgia. In addition, other AEs that have been generally associated with approved IM administered vaccines have included mild hematological and clinical chemistry abnormalities, which are usually reversible.

The investigational vaccines should not be administered to individuals with a known hypersensitivity to any component of the study product. There is also a potential risk of hypersensitivity reactions following the administration of any study product.

Several animal studies with experimental whole-virus inactivated and subunit vaccines of other coronaviruses have shown enhanced immunopathology in a greater number of vaccinated animals compared to controls upon subsequent virus infection. These experimental vaccines often exhibited Th2-biased immune responses or elicited antibodies that had poor neutralizing activity against the virus. In preclinical studies of Gritstone's SAM, a predominant Th1-focused immune response was observed.

The relevance of these observations in humans is unknown. Notably, most people during their lifetimes have likely been infected with one or more of the 4 endemic strains of human coronaviruses (hCoV 229E, NL63, OC43, and HKU1) that circulate globally and are responsible for 10-30% of mild to moderate upper respiratory tract infections. Despite the likelihood of cross-reactive antibody responses with poor functional activity, no evidence of enhanced CoV disease in humans has ever been reported.

4.3.4 Risks to Privacy

Subjects will be asked to provide data concerning health. This information will be kept confidential within the limits of the local law and consistent with the guidelines of the General Data Protection Regulation (EU) 2016/279 of the European Parliament (“GDPR”) and the Health Insurance Portability and Accountability Act for US sites. All study records in physical form will be kept in a locked file cabinet or maintained in a locked room at the participating site, with controlled entry to prevent unauthorized access. Electronic files will be password protected and encrypted at rest and in transit. Only people who are involved in the conduct, oversight, monitoring, or auditing of this trial will be allowed access to the health data that is collected. Any publications from this trial will not use information that will identify subjects by name, and such information may be anonymized, pseudonymized, or de-identified as applicable. Organizations that may inspect and/or copy research records maintained at the participating site for quality assurance (QA) and data analysis include groups such as Gritstone's and its affiliates, the Ethics Committee (EC), and the Medicines and Healthcare Products Regulatory Agency (MHRA) and will be subject to strict confidentiality provisions regarding any patient data.

4.3.5 Risks of Genetic Testing

[figure not shown]
Any genetic data generated will be kept private. There may be a risk that information resulting from research genetic testing could be misused for discriminatory purposes. However, national laws provide protections against genetic discrimination. Researchers will need to maintain confidentiality in order to be granted access to genetic information.

4.3.6 Known Potential Benefits

There is no direct benefit to the subjects. There is potential benefit to society resulting from insights gained from participation in this study due to the on-going threat of the SARS-CoV-2 outbreak. Vaccination using Gritstone's investigational vaccines may or may not provide protection against infection by SARS-CoV-2. The duration of any such protection is currently unknown.

5 OBJECTIVES AND ENDPOINTS

Objectives	Endpoints (Outcome Measures)
Primary	
To assess the safety and tolerability of 2 different doses (10 or 30 mcg) of GRT-R910 when administered to healthy adults ≥ 60 years of age who were previously vaccinated with a first-generation COVID-19 vaccine (Cohorts 1 and 2; AstraZeneca)To assess the safety and tolerability of a 10 mcg dose of GRT-R910 when administered to healthy adults (≥ 18 years of age) who were previously vaccinated with an mRNA-based COVID-19 vaccine (Pfizer/BioNTech, Moderna)
Secondary	
To assess the cellular and humoral immunogenicity of GRT-R910 when administered to volunteers (≥ 60 years of age for Cohorts 1, 2, 3, and 4 and ≥ 18 to ≤ 59 years of age for Cohort 6) who were previously vaccinated with an mRNA-based COVID-19 vaccine (Pfizer/BioNTech, Moderna)
[REDACTED]	[REDACTED]

6 STUDY DESIGN

6.1 Overall Design

This is a multi-center, open-label, dose-escalation design study to examine dose, safety, tolerability, and immunogenicity of GRT-R910, an investigational SAM SARS-CoV-2 vaccine when administered to healthy adults 18 years and older who were previously vaccinated with a first-generation COVID-19 vaccine (Cohorts 1 and 2; AstraZeneca), an adenoviral COVID-19 vaccine (Cohort 3; AstraZeneca, Janssen), or an mRNA-based COVID-19 vaccine (Cohorts 4 and 6; Pfizer/BioNTech, Moderna) ([Figure 1](#)).

[figure not shown]
In Cohorts 1 and 2, healthy adults ≥ 60 years of age (N=10, including 2 sentinels per cohort) will receive 2 doses of GRT-R910 (homologous prime-boost) at 1 of 2 dose levels (10 mcg or 30 mcg) at least 2 months after receiving AstraZeneca's COVID-19 prime and boost vaccine. The GRT-R910 booster dose will be administered 113 days (16 weeks) after the prime. In Cohorts 3 and 4, healthy adults ≥ 60 years of age (N=10) will receive 2 doses of GRT-R910 (homologous prime-boost) 10 mcg (dose selected from Cohorts 1 and 2) at least 2 months after receiving an adenoviral COVID-19 vaccine (Cohort 3; AstraZeneca, Janssen), or an mRNA-based COVID-19 vaccine (Cohort 4; Pfizer/BioNTech, Moderna). In Cohort 6, healthy adults ≥ 18 to ≤ 59 years of age (N=10) will receive 2 doses of GRT-R910 (homologous prime-boost) 10 mcg (dose selected from Cohorts 1 and 2) at least 2 months after receiving an adenoviral COVID-19 vaccine or an mRNA-based COVID-19 vaccine (Cohort 6; Pfizer/BioNTech, Moderna). The GRT-R910 booster dose will be administered 28 days after the prime.

Sentinel dosing in Cohorts 1 and 2 will consist of 2 volunteers in each cohort dosed 72 hours ahead of the remainder of each cohort, with the remainder of the volunteers dosed at the same dose level only if no halting rules are met. Enrollment in Cohort 2 will only proceed if safety data from all volunteers in Cohort 1 meet the dose-escalation rules. There will be no sentinel dosing in Cohorts 3, 4, and 6. The dose for Cohorts 3, 4, and 6 was selected from Cohorts 1 and 2 after evaluation of reactogenicity, safety, and initial immunogenicity. Dose selection will be determined by the Gritstone clinical team in consultation with the PI(s).

The reactogenicity and immunogenicity data assessed after the first dose of GRT-R910 will inform selection of the GRT-R910 dose to be tested in future studies. The 10 mcg dose of GRT-R910 was selected for use in Cohorts 3, 4, and 6 by evaluating the balance of immunogenicity and reactogenicity of a single dose of GRT-R910 in Cohorts 1 and 2.

Injection will be given intramuscularly as a prime-boost at least 2 months after the last administration of a SARS-CoV-2 vaccine either approved for emergency supply or approved for use by the MHRA for prevention of SARS-CoV-2. Subjects should refrain from a subsequent boost with an emergency supply or approved SARS-CoV-2 vaccine for a minimum of 4 months after the second dose of study vaccine.

Figure 1 Study Flow Chart

6.2 Dose Justification

GRT-R910 will be assessed at doses of 10 mcg and 30 mcg. Dose justification is discussed in [Section 4.3.1](#).

6.3 End of Study Definition

Subjects from Cohorts 1 and 2 (NOT receiving booster dose) will be followed for 12 months, subjects from Cohorts 1 and 2 (receiving booster dose) will be followed for 16 months, subjects from Cohorts 3 and 4 will be followed for up to 13 months, and subjects from Cohort 6 will be followed for 7 months. Vaccinated subjects will be carefully monitored for exposure and infection to SARS-CoV-2 throughout the study.

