3.2 Schedules of Assessments

Table 1 Schedule of Assessments: Cohorts 1 and 2 – Subjects NOT Receiving Booster Dose

Study Visit	V00	V01	V02	V03	V04	V05	V06	V07	V08	Unsch Visit	Early Term Visit
Study Day(s)	SCR -30 to -1	Day 1	Day 2 +1d	Day 4 +2d	Day 8 +2d	Day 29 ±3d	Day 57 ±3d	Day 180 ±3d	Day 365 ±7d		
Obtain Written Informed Consent	X										
Review Eligibility Criteria	X	X									
Medical History	X										
Review of Interim Medical History		X	X	X	X	X	X	X	X	X	X
Concomitant Medications	X	X	X	X	X	X	X	X	X	X	X
Vital Signs (Oral Temp, Pulse, BP)	X	X			X	X	X	X	X	X	X
Physical Examination Including Height and Weight	X										
Targeted Physical Examination, if Indicated		X			X	X	X	X	X	X	X
Nasal Swab Collection for SARS-CoV-2 PCR	X										X ⁷
Blood Collection for Safety Labs	X ¹				X ²		X ²	X ²		X ²	X ²
Blood Collection for HBsAg, Anti-HCV, SARS-CoV-2 Serology ³ , HIV	X						X ³				
Blood Collection for Cellular Immune Assays		X			X	X		X	X	X	X
Blood Collection for Antibody Assays		X				X	X	X	X	X	X
Vaccination		X									
45 Minute Evaluation After Study Vaccination		X									
Distribute Memory Aid and Study-Related Materials		X									
Review Memory Aid			X	X	X					X ⁴	X ⁴

Study Visit	V00	V01	V02	V03	V04	V05	V06	V07	V08	Unsch Visit	Early Term Visit
Study Day(s)	SCR -30 to -1	Day 1	Day 2 +1d	Day 4 +2d	Day 8 +2d	Day 29 ±3d	Day 57 ±3d	Day 180 ±3d	Day 365 ±7d		
Adverse Events		X	X	X	X	X				X ⁵	X ⁵
SAEs/AESIs Including PIMMCs/MAAEs/NOCMCs ⁸		X ⁹	X	X	X	X	X	X	X	X	X
Phone Visit ⁶			X	X							
Saliva Collection for Antibodies		X			X			X			

Abbreviations: AESI, adverse event of special interest; BP, blood pressure; HBsAg, hepatitis B surface antigen; HCV, hepatitis C virus; HIV, human immunodeficiency virus; MAAE, Medically Attended Adverse Event; NOCMC, New Onset Chronic Medical Condition; SAE, serious adverse event; PCR, polymerase chain reaction; PIMMC, Potentially Immune-Mediated Medical Condition; SARS-CoV-2, severe acute respiratory syndrome coronavirus 2; SCR, screening; Unsch, unscheduled

- Includes white blood cells (WBCs), hemoglobin (Hb), platelets (PLT), alanine aminotransferase (ALT), aspartate aminotransferase (AST), alkaline phosphatase (ALP), total bilirubin, creatine kinase (CK), serum creatinine, prothrombin time (PT)/international normalized ratio (INR), and activated partial thromboplastin time (aPTT)
- Includes WBCs, Hb, PLT, ALT, AST, ALP, total bilirubin, CK, and serum creatinine
- Includes SARS-CoV-2 serology (N-specific) only

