- If within 7 days after vaccination
- If prior to Visit 05
- Can be phone, text, or e-mail contact
- A nasal swab for SARS-CoV-2 should be performed within 3 days of COVID-19 symptoms and repeated after 7 days.
- AESIs, including serologically or virologically confirmed SARS-CoV-2 infection and severity of COVID-19, PIMMCs, MAAEs, and NOCMCs will be collected from the time of first vaccination throughout the entire study.
- SAEs occurring after signing of the informed consent form (ICF) will be recorded and reported to the sponsor or designee by the investigator within 24 hours of becoming aware of the SAE.

Table 2 Schedule of Assessments: Cohorts 1 and 2 – Subjects Receiving Booster Dose

Study Visit	V00	V01	V02	V03	V04	V05	V06	V07	V08	V09	V10	V11	V12	V13	V14	Unsch Visit	Early Term Visit
Study Day(s)	SCR -30 to -1	Day 1	Day 2 +1d	Day 4 +2d	Day 8 +2d	Day 29 ±3d	Day 57 ±3d	Day 113 ¹² -3d/+21d	Day 114 +1d	Day 116 +2d	Day 120 +2d	Day 142 ±3d	Day 170 ±3d	Day 293 ±3d	Day 478 ±7d		
Obtain Written Informed Consent	X																
Review Eligibility Criteria	X	X						X									
Medical History	X																
Review of Interim Medical History		X	X	X	X	X	X	X	X	X	X	X	X	X	X	X	X
Concomitant Medications	X	X	X	X	X	X	X	X	X	X	X	X	X	X	X	X	X
Vital Signs (Oral Temp, Pulse, BP)	X	X			X	X	X	X			X	X	X	X	X	X	X
Physical Examination Including Height and Weight	X																
Targeted Physical Examination, if Indicated		X			X	X	X	X			X	X	X	X	X	X	X
ECG ⁸		X ⁹			X	X	X	X ⁹			X	X	X	X	X		
Cardiac Biomarkers (Troponin T, CRP, ESR) ¹⁰		X ¹¹			X	X	X	X ¹¹			X	X	X	X			
Nasal Swab Collection for SARS-CoV-2 PCR	X															X ⁷	
Blood Collection for Safety Labs	X ¹				X ²		X ²				X ²		X ²	X ²		X ²	X ²
Blood Collection for HBsAg, Anti-HCV, SARS-CoV-2 Serology ³ , HIV	X						X ³						X ³				

Study Visit	V00	V01	V02	V03	V04	V05	V06	V07	V08	V09	V10	V11	V12	V13	V14	Unsch Visit	Early Term Visit
Study Day(s)	SCR -30 to -1	Day 1	Day 2 +1d	Day 4 +2d	Day 8 +2d	Day 29 ±3d	Day 57 ±3d	Day 113 ¹² -3d/+21d	Day 114 +1d	Day 116 +2d	Day 120 +2d	Day 142 ±3d	Day 170 ±3d	Day 293 ±3d	Day 478 ±7d		
Blood Collection for Cellular Immune Assays		X			X	X		X				X		X	X	X	X
Blood Collection for Antibody Assays		X				X	X	X				X		X	X	X	X
Vaccination		X						X									
45 Minute Evaluation After Study Vaccination		X						X									
Distribute Memory Aid and Study-Related Materials		X						X									
Review Memory Aid			X	X	X				X	X	X				X ⁴	X ⁴	
Adverse Events		X	X	X	X	X		X	X	X	X				X ⁵	X ⁵	

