SAEs/AESIs Including PIMMCs/MAAEs/NOCMCs ¹³	X ¹⁴	X	X	X	X	X	X	X	X	X	X	X	X	X	X	X	X
Phone Visit ⁶			X	X					X	X							
Saliva Collection for Antibodies		X			X			X			X			X			

Abbreviations: AESI, adverse event of special interest; BP, blood pressure; d, day(s); ECG, electrocardiogram; HBsAg, hepatitis B surface antigen; HCV, hepatitis C virus; HIV, human immunodeficiency virus; MAAE, Medically Attended Adverse Event; NOCMC, New Onset Chronic Medical Condition; SAE, serious adverse event; PCR, polymerase chain reaction; PIMMC, Potentially Immune-Mediated Medical Condition; SARS-CoV-2, severe acute respiratory syndrome coronavirus 2; SCR, screening; Unsch, unscheduled

- Includes white blood cells (WBCs), hemoglobin (Hb), platelets (PLT), alanine aminotransferase (ALT), aspartate aminotransferase (AST), alkaline phosphatase (ALP), total bilirubin, creatine kinase (CK), serum creatinine, prothrombin time (PT)/international normalized ratio (INR), and activated partial thromboplastin time (aPTT)
- Includes WBC, Hb, PLT, ALT, AST, ALP, total bilirubin, CK, and creatinine
- Includes SARS-CoV-2 serology (N-specific) only
- If within 7 days after each vaccination (prime or boost dose)

- 5 If prior to Visit 11
- 6 Can be phone, text, or e-mail contact
- 7 A nasal swab for SARS-CoV-2 should be performed within 3 days of COVID-19 symptoms and repeated after 7 days.
- 8 ECG will be performed for subjects receiving booster dose in Cohorts 1 and 2. ECG data will include heart rate and RR, PR, QT, and QRS durations.
- 9 ECG will be performed before 1st and 2nd doses of vaccination.
- 10 Cardiac biomarker assessment will be performed for subjects receiving booster dose in Cohorts 1 and 2. Cardiac biomarker assessments will include troponin T, C-reactive protein (CRP), and erythrocyte sedimentation rate (ESR).
- 11 Cardiac biomarker assessment will be performed before 1st and 2nd doses of vaccination.
- 12 In case of second dose delay (allowed -3 days/+21 days), all safety visits (Visit 08 to Visit 12) will be scheduled based on the day of the second dose (e.g., Visit 08 will occur 1 day after delayed second dose and not on Day 114). All visits will shift based on the second dose without changing the time interval between 2 consecutive visits.
- 13 AESIs, including serologically or virologically confirmed SARS-CoV-2 infection and severity of COVID-19, PIMMCs, MAAEs, and NOCMCs will be collected from the time of first vaccination throughout the entire study.

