11 ASSESSMENT OF SAFETY

11.1 Assessing and Recording Safety Parameters

Safety will be assessed by the frequency and severity of:

- SAEs occurring from the time of study consent throughout the entire study (reported to the sponsor or designee by the investigator within 24 hours of becoming aware of the SAE);
 - If the SAE occurs after signing of the ICF and before the first (prime) dose, it will be reported on the medical history eCRF. If the SAE occurs after the first (prime) dose, it will be reported on the AE eCRF.
- Solicited AEs (reactogenicity events occurring from the time GRT-R910 vaccination through 7 days after GRT-R910 vaccination);
- Reactogenicity local reactions (including erythema, induration/edema, pain, and tenderness);
- Reactogenicity systemic reactions (including fever, chills, fatigue, malaise, myalgia, arthralgia, headache, and nausea);
- Clinical safety laboratory AEs occurring from the time of GRT-R910 vaccination through approximately 7 days after GRT-R910 vaccination (parameters to be evaluated include WBC, Hb, PLT, ALT, AST, ALP, total bilirubin, CK, and creatinine);
- Unsolicited AEs (non-serious AEs occurring from the time of GRT-R910 vaccination through approximately 28 days after GRT-R910 vaccination);
- AESIs (including serologically or virologically confirmed SARS-CoV-2 infection and severity of COVID-19, PIMMCs, MAAEs, and NOCMCs occurring from the time of the first study vaccination throughout the entire study).

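### Cohorts 1 and 2 have no scheduled N-specific serology for about the last 308 days, so asymptomatic infection in that period is under-ascertained

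*Protocol*

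**What the plan says.** Protocol 6.3 commits to infection monitoring for the whole study: "Vaccinated subjects will be carefully monitored for exposure and infection to SARS-CoV-2 throughout the study". Protocol 11.1 lists among the safety measures "AESIs (including serologically or virologically confirmed SARS-CoV-2 infection and severity of COVID-19", collected from first vaccination to the end of the study; 11.1.5 repeats the definition. AESIs throughout the study belong to the primary outcome measures, and planned SAP Table 14.3.1.22 tabulates serologically or virologically confirmed events over the same period.

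The schedules in Protocol 3.2 have a row headed "Blood Collection for HBsAg, Anti-HCV, SARS-CoV-2 Serology" and HIV. The post-dose marks in that row carry footnote 3, "Includes SARS-CoV-2 serology (N-specific) only". Table 1 (no booster) marks screening and V06, Day 57. Table 2 (booster) marks screening, V06 and V12, Day 170. SAP Tables 6 and 7 carry the same marks. Nothing is marked at V07 and V08 in Table 1, at V13 and V14 in Table 2, or at unscheduled or early-termination visits. After screening, the nasal swab for PCR is tied to COVID-19 symptoms.

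On duration, 6.3 says "Subjects from Cohorts 1 and 2 (NOT receiving booster dose) will be followed for 12 months" and "subjects from Cohorts 1 and 2 (receiving booster dose) will be followed for 16 months".

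**The concern.** PCR after screening depends on symptoms, so N-specific serology is the only scheduled way to find an infection without symptoms. In Cohorts 1 and 2 it stops long before follow-up does. Two uses of the data are affected.

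- **Incidence.** The second metric in SAP 8.1 counts AEs coded to COVID-19 terms, including asymptomatic COVID-19. Its person-days run from the prime dose to the event, the end of participation or the data cutoff, whichever is earliest. The late period enters the denominator in full, while no scheduled test can add an asymptomatic event to the numerator.
- **Late immunogenicity.** Durability is part of the vaccine's rationale, and the late antibody and T-cell samples fall inside the gap. An unrecognised infection could raise those values and be read as a persisting vaccine response. With 10 subjects per cohort, a few such subjects could shift a geometric mean.

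**Working it through.** **Inputs** (Protocol Tables 1 and 2; SAP Tables 6 and 7 agree on the serology marks):

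| | Last N-specific serology | Last visit |
|---|---|---|
| No booster | V06, Day 57 ± 3 | V08, Day 365 ± 7 |
| Booster | V12, Day 170 ± 3 | V14, Day 478 ± 7 |

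**Stated follow-up first**, as (last day − 1) / 30.4375:

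- No booster: 364 / 30.4375 = 11.96 months (stated 12).
- Booster: 477 / 30.4375 = 15.67 months (stated 16).

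The visit days therefore match the stated durations.

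**Gap** = last visit day − day of last N-specific serology:

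- No booster: 365 − 57 = 308 days.
- Booster: 478 − 170 = 308 days.
- Shortest with windows: (365 − 7) − (57 + 3) = 298, and (478 − 7) − (170 + 3) = 298.
- Longest with windows: (365 + 7) − (57 − 3) = 318, and (478 + 7) − (170 − 3) = 318.

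A delayed second dose does not change the booster figure, because "All visits will shift based on the second dose without changing the time interval between 2 consecutive visits".

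**Share of post-prime follow-up** for a subject who completes without an event:

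- No booster: 308 / 364 = 85%.
- Booster: 308 / 477 = 65%.

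**Samples inside the gap.** Blood for antibody assays and for cellular assays is drawn at Days 180 and 365 (Table 1) and at Days 293 and 478 (Table 2). Protocol 10.2.2 assigns the serum to antibody binding and pseudovirus neutralisation. The visible text does not name N among the antigens.

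**Other cohorts.** SAP Table 8 marks serology at screening and V12 (Day 209) for Cohorts 3, 4 and 6. For Cohorts 3 and 4 the gap to the conditional V13 is 394 − 209 = 185 days. Cohort 6 ends at Day 209 and has no gap. The matching row of Protocol Table 3 is not in the text available, so this part rests on the SAP alone.

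**The case against.** The AESI can be confirmed by serology or by virology, and the second route stays open to the last visit: a swab within 3 days of symptoms, repeated after 7 days, with interim history and AESI review at every visit. A reader might infer that infection monitoring lapses for 308 days, or that this primary-endpoint component fails. The documents do not support that. They promise monitoring and AESI collection throughout, not serology throughout. What remains is asymptomatic or unswabbed infection.

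A reader might also infer that late immune responses cannot be separated by infection status. That goes too far. Part of Protocol 10.2.2 is redacted, the antigens of the binding assay are not named, and immunogenicity has its own SAP, which is not available here. Protocol 13.2.1 also foresees stored samples being used to study subjects who become seropositive during the trial. That is possible secondary research, so it softens the gap without closing it.

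The consequences for inference are modest. Protocol 12.1 rules out hypothesis tests between cohorts, and SAP 8.1 uses PCR results and AE terms, so serology enters only when a positive result is recorded as an AE.

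It is tempting to give a count of missed infections. An assumed attack rate of 10 to 30% would give 1 to 3 of 10 subjects, but that only restates an assumption with no source in the documents.

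Finally, SAP 9.2 lists N-specific serology as a local-laboratory test, whereas antibody serum is a research sample. Nothing shows that one tube has enough volume for both.

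**Conclusion.** The point holds in this limited form. Cohorts 1 and 2 have a nominal 308 days (298 to 318) with no scheduled N-specific serology, which is 85% of post-prime follow-up without the booster and 65% with it. The 85% applies only to subjects who do not receive the second dose; the documents do not give their number.

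Within that period asymptomatic or unswabbed infection is under-ascertained, the AE-based incidence rate is biased downward for such events, and late antibody and T-cell values may include unrecognised infection. The size of these effects is unknown.

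The conclusion assumes that no redacted text assigns N testing to the late samples, and it accepts the protocol's own post-dose use of N-specific serology as a marker of infection. It is a cheap improvement to ascertainment and interpretation, not evidence that the primary safety analysis is invalid.

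**What to change.** 1. Add N-specific serology at V07 and V08 in Protocol Table 1 and at V13 and V14 in Table 2. Add it at the conditional V13 of Cohorts 3 and 4 in Table 3, after checking the existing marks in that row. Make the same changes in SAP Tables 6 to 8.
2. Run it on serum already drawn for antibody assays. For completed visits use stored serum; Protocol 13.2.2.2 allows amendments with additional assays to use repository samples.
3. Amend the statement in SAP 9.2 that leaves serology unsummarised, so that post-baseline N seroconversion is summarised by cohort. Otherwise the new results would reach only listings and AE entries.
4. If redacted text in 10.2.2 already assigns N testing to these samples, cross-refer to it from the schedules instead of adding assays.

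Cost: 20 subjects × 2 visits = 40 assays in Cohorts 1 and 2, plus up to 20 × 1 = 20 in Cohorts 3 and 4, so about 40 to 60. No extra visit is needed. Whether an extra draw can be avoided depends on residual serum volume, which the documents do not give. Expect a protocol amendment and a few late AESI entries.
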